9.1.1 Relationship of Adverse Events to Study Drug

Investigators will not be required to assess the causality of solicited AEs if the onset is during the solicitation period.

The investigator will determine the causal relationship between the study vaccine and the AE for all unsolicited AEs, SAE, MAAE and AESIs. The relationship of unsolicited AEs to the study vaccine (Yes, No) will be captured on the eCRF.

The number and percentage of participants along with the frequency of AEs (unsolicited AEs and SAEs) by SOC, PT, and relationship will be produced.

A participant with 2 or more AEs within the same SOC or PT level but different relationship will be counted only once in the level using the related incident. If the causality is missing, then a “missing” category will be included in the summary.

9.1.2 Severity of Adverse Event

The severity of AEs (mild, moderate, severe) will be captured on the eCRF. Adverse events (unsolicited AEs, solicited AEs, and SAEs) will be summarized including the number of participants and percentages by dose group, study vaccine, as well as by SOC, PT, and severity. If the severity is missing, then a “missing” severity category will be included in the summary. A participant with 2 or more AEs within the same SOC or PT level but different severity will be counted only once at the most severe level.

9.1.3 Outcome of Adverse Event

The outcome of an AE will be assessed as at the time of last observation per the following categories:

- Fatal
- Not Recovered/ Not Resolved
- Recovered/Resolved
- Recovered/Resolved with sequelae
- Recovering/Resolving
- Unknown

The number and percentage of participants along with the frequency of adverse events (unsolicited, AESIs, MAAEs and SAEs) will be summarized by SOC, PT, and outcome.

A participant with 2 or more AEs within the same SOC or PT level but different outcome will be counted only once with higher outcome grading.

9.1.4 Solicited Adverse Event

Solicited AEs are prespecified local and systemic. Solicited AEs will be collected from day 1 through 7 days following the vaccination (day 1-7) using eDiary. Solicited AEs with onset during the 7-day solicitation period that continue beyond the 7-day period will be reported as unsolicited AEs.

The following specific solicited adverse events will be used to assess reactogenicity.

Local reactions at injection site:

- Injection Site Pain
- Redness
- Swelling
- Lymphadenopathy (localized axillary, cervical or supraclavicular swelling or tenderness ipsilateral to the vaccination arm)

Systemic reactions:

- Fever
- Headache
- Fatigue
- Myalgia
- Arthralgia
- Chills

The number and percentage of participants with any local solicited AEs, and systemic solicited AEs will be presented for each age group and dose group among participants with eDiary information available.

All solicited AEs local and systemic will be listed by age and participant number. Solicited adverse events reported until 7 days (day 1 through day 7) postvaccination will be summarized by maximum severity and by dose group.

Prolonged Solicited AEs that continue beyond day 7 will be reported on the eCRF as Unsolicited AEs and will be listed as such. The number and percentage of participants with prolonged solicited AE will be presented for each age group (any, any local, any systemic, each solicited AE).

In addition, the duration (in days) of solicited AEs which started within day 1-7 will be summarized by dose group for each age group. The duration for any severity will be calculated as Stop date – Start date + 1, where start date is the first day with AE while stop is the last day with the AE in or beyond the solicited period. The

duration of solicited AE with specific severities (mild/moderate/severe, moderate/severe, severe) will be the number of days with the severity.

Currently on the eCRF the investigator can overwrite the severity of AEs on the eDiary, if he believes the event grading has not been recorded, has been underestimated or overestimated, and provide his assessment. When available the severity provided by the investigator will be used instead of the eDiary grading to generate the summaries of solicited events.

The percentage of eDiary days completed will be summarized by dose and age group. A day is considered completed in the eDiary if it was entered by the participant or the investigator. The percentage of completed days will be calculated as follows:

$$\text{SumSymp}/(7*\text{NumSymp}*\text{ExpSubj})$$

SumSymp is the sum of the total number of days completed for a specific symptom across all symptoms and exposed subjects. NumSymp is the number of symptoms and ExpSubj is the number of exposed subjects.

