**Table 3-2 Dosing Scenarios for Participants Enrolled in Cohorts 4 and 5**

Dosing Scenario	Group 4a OR 4b	Group 5a OR 5b
#1	75 µg	100 µg
#2	100 µg	150 µg
#3	100 µg	200 µg

While the SRT reviews safety data, enrollment in the same group will continue until the cohort is full. The SRT recommendation for each group could be to escalate to the next dose level or to stop the enrollment at the current dose.

At each SRT meeting, a Bayesian logistic regression model (Section 13.3) will be used to predict unacceptable reactogenicity at the current or next dose level. A lower than 50% posterior probability that the percentage is above the maximum tolerable rate will be favorable to progression to the next higher dose. Based on the historical Phase 1 reactogenicity data from [redacted] vaccines, the maximum tolerable rate for Grade 3 solicited adverse events has been set to 30%. The SRT may recommend dropping groups at any time during the study if an

[figure not shown]
unfavorable safety profile is observed in that group or based on safety or immunogenicity data from other groups.

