2.1. Primary Objective and Endpoints

Objectives	Endpoints
Primary – Safety	
To evaluate the safety and tolerability of CV0501 at each dose level	
 Percentage of participants with each solicited local and systemic AEs during 7 days after vaccination (i.e., the day of study vaccination and 6 subsequent days (day 1 through 7) Percentage of participants with each abnormal clinical safety laboratory finding for 8 days after study vaccination Percentage of participants with unsolicited AEs for 28 days after study vaccination Percentage of participants with MAAEs, AESIs and SAEs from study vaccination through the end of the study (for 180 days after the study vaccine administration), each summarized separately

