3.4. Dose Adjustment/Modifications

An overdose is any dose of study vaccine given to a participant that exceeds the planned dose for an individual within a given dose group.

There is no specific treatment recommended for an overdose. Overdose itself is not to be reported as an adverse event (AE). Overdose participants will be included in the Safety Set and excluded from Per protocol Immunogenicity (PPI) Set.

4. General Statistical Considerations

Participants will be identified in the listings by the participant identification number concatenated with the site number. Data will be displayed in all listings sorted by age group, dose group and participant number.

Continuous data will be described using descriptive statistics (n, mean, standard deviation, median, minimum, and maximum).

Categorical data will be described using the participant count and percentage for each category.

For the **summary statistics** of all numerical variables unless otherwise specified, mean, confidence interval, median, standard deviation, minimum and maximum will be displayed.

A row denoted “Missing” will be included in count tabulations where specified on the shells to account for dropouts and missing values.

There is no formal hypothesis testing in this study where statistical methods are applied, the emphasis will be on estimation with 2-sided 95% Confidence intervals (CIs).

The denominator for all percentages will be the number of participants with non-missing values of corresponding parameter in that treatment within the analysis population of interest, unless otherwise specified.

A table, figure, listing (TLF) is to be generated for any required item even where no data is available or reported. In such cases, the table, figure or listing will state: “**No Data Reported**”. This will confirm to the health authorities that all data for the tables, figures, listings, and narratives are accounted for.

Baseline will be defined as the last non-missing evaluation prior to study vaccine administration, unless otherwise specified.

Study day will be calculated as follows:

- study day prior to the injection will be calculated as: date of assessment – date of the injection
- study day on or after the date of the injection will be calculated as: date of assessment – date of the injection + 1

For Safety assessment of AEs, the intervals will be calculated as follow

- solicited AEs: the day of vaccination and 6 subsequent days (day 1 through 7)

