The GMT at each postvaccination time point, the GMI from baseline, and the 95% CIs in all cohorts will be analyzed using an ANCOVA model on log10 transformed titers with dose group and age group as fixed in the model and prior Covid-19 infection and prevaccination baseline value as covariates.

[figure not shown]
8.2.2. Seroresponse rate 28 days after the booster dose (day 29), based on neutralizing Ab titers against pseudoviruses bearing S protein from SARS-CoV-2 WT, Omicron BA.1, BA.2 and BA.5 variants at each collection timepoint, with seroresponse defined as postboost titers $\geq 4 \times$ preboost titers.

Proportion of participants with neutralizing seroresponse of serum SARS-CoV-2 WT, Omicron BA.1, BA.2 and BA.5 variants specific Ab from baseline at day 29 by dose group and prior Covid-19 infection will be tabulated with 2-sided 95% Clopper Pearson CIs. The same summaries will be generated for seroresponse rate 14 days after booster dose (Day 15) as supportive analyses.

[figure not shown]
CCI

CCI

CCI

Approved

CCI

9 Safety Analysis

Safety, tolerability, and reactogenicity will be assessed by clinical review of all relevant parameters including solicited and unsolicited AEs, SAEs, AESIs, MAAEs, AEs leading to withdrawal from study participation, safety laboratory test results, vital signs, and physical examination findings.

All safety analyses will be based on Safety Set. All safety analyses will be provided by dose group and age group unless otherwise specified.

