9.1 Adverse Events

An AE is any untoward medical occurrence in a participant enrolled into this study regardless of its causal relationship to the IP. This definition includes exacerbations of pre-existing conditions. Stable pre-existing conditions which do not change in nature or severity during the study are not considered AEs; however, these should be reported as part of the medical history at screening.

SOC will be displayed in alphabetical order. PT will also be displayed alphabetically within SOC. Percentages will be based upon the number of participants in the Safety Set within each dose group.

Incomplete AE onset date/time and end date will be imputed following the rules below.

Missing Start Dates

If day is missing and month and year are available:

- UK-MMM-YYYY: Assume 01-MMM-YYYY (first day of the month), but if month and year are the same as the first study vaccination month and year, then assume the date of first vaccination.

If day and month are missing and year is available:

- UK-UKN-YYYY: Assume 01-JAN-YYYY (first day of the year), but if year is the same as the first study vaccination year, then assume the date of first study vaccination.

If day, month and year (date) are missing:

- UK-UKN-UNKN: Assume date of first study vaccination.

Missing Stop Dates

If day missing and month and year are available:

- UK-MMM-YYYY: Assume the last day of the month

If day and month are missing and year is available:

- UK-UKN-YYYY: Assume 31-DEC-YYYY

If day, month and year (date) are missing:

- UK-UKN-UNKN: Do not impute and assume ongoing

All adverse events will be classified by SOC and PT according to the MedDRA.

Unless otherwise specified, AEs will be summarized by dose group based on Safety Set. A listing of AEs will be provided by age group, dose group and participant number.

All events from screening until vaccination will be considered as medical history.

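### The SAP gives conflicting denominators for solicited-AE percentages and names none for the Grade 3 summary; the Safety Set rule, if applied, counts a participant with no diary data as reaction-free

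*SAP*

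**What the plan says.** The first primary endpoint (SAP 2.1) is "Percentage of participants with each solicited local and systemic AEs during 7 days after vaccination", so it is defined symptom by symptom. Several SAP sentences bear on its denominator.

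- Section 4, a default that yields wherever another rule is given: "The denominator for all percentages will be the number of participants with non-missing values of corresponding parameter in that treatment within the analysis population".
- Section 9, which sets the population: "All safety analyses will be based on Safety Set".
- Section 9.1: "Percentages will be based upon the number of participants in the Safety Set within each dose group". Section 9.1.2 sits under it, lists solicited AEs among the events tabulated with percentages by severity, and states no denominator of its own.
- Section 9.1.4: the any-local and systemic percentages "will be presented for each age group and dose group among participants with eDiary information available". This is the only sentence that restricts a solicited-AE percentage to people with diary data. It covers neither individual symptoms nor grades.
- Section 9.1.4, next paragraph: "Solicited adverse events reported until 7 days (day 1 through day 7) postvaccination will be summarized by maximum severity and by dose group". It names no denominator.
- Section 8.1.1 gives the primary percentages by dose group, also without a denominator.

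Protocol 7.6 leaves missing reactogenicity data to the SAP, and the SAP has no rule for a vaccinated participant without a diary. The missing category in 9.1.2 is for an event without a grade, not for a participant without data.

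Protocol 3.1.1 adds that "the maximum tolerable rate for Grade 3 solicited adverse events has been set to 30" percent. Protocol Appendix 13.3 applies that limit through a Bayesian logistic model.

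**The concern.** Solicited AEs come from the diary. A vaccinated participant with no diary entries has an unknown reaction status, not a negative one. Put in the denominator with nothing in the numerator, that participant becomes a non-reactor by arithmetic. The resulting error runs one way, toward better tolerability, and is larger in whichever dose or age group completes fewer diaries. The SAP expects some incompleteness, because 9.1.4 plans a completion summary by dose and age group.

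Reactogenicity is a primary endpoint and informs dose selection. Two programmers working from this text could produce different Grade 3 rates for the same data. The any-reaction table and the severity table in one report could also rest on different denominators.

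**Working it through.** **1. Which rule governs which output**

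| Output | Denominator named | Rules that could apply |
|---|---|---|
| Any local, systemic (9.1.4) | eDiary available | eDiary available |
| Maximum severity by dose (9.1.4) | none | 9.1 Safety Set; 9.1.4 eDiary by extension; section 4 |
| Severity by SOC and PT, including solicited AEs (9.1.2) | none | 9.1 Safety Set |
| Primary percentages (8.1.1) | none | section 4 non-missing; 8.1.1 is outside 9.1 |
| Each symptom (endpoint in 2.1) | none | any of the three |

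**2. Size of the difference**

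Let N be the Safety Set count, m the number with no diary data and x the number with a Grade 3 event. Then x/N = x/(N − m) × (N − m)/N, so the Safety Set rate is the diary-based rate times the share with diary data. Group sizes come from the protocol (10 is the minimum for a safety review, 15 and 30 are cohort sizes). The values of x and m are assumptions, because neither document gives a missing-diary rate.

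| N | x | x/N | x/(N − m) |
|---|---|---|---|
| 30 | 9 | 30.0% | m=0: 30.0%; m=1: 31.0%; m=3: 33.3% |
| 15 | 4 | 26.7% | m=1: 28.6%; m=2: 30.8% |
| 10 | 3 | 30.0% | m=1: 33.3%; m=2: 37.5% |

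Put as a proportion, a diary-based 33% becomes 0.33 × 0.95 = 31.4% with 5% missing, 0.33 × 0.90 = 29.7% with 10%, and 0.33 × 0.80 = 26.4% with 20%.

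**3. Reproducing the protocol's model**

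Inputs are the Appendix 13.3 two-component prior, reference dose 50 µg, no age term, and 0 events entered as 1 as the Table 13-2 footnote says. The posterior was found by numerical integration on a grid. For scenario 2, the next-dose probabilities that the rate exceeds 30% come out at 0.017, 0.373, 0.641 and 0.825. Table 13-2 gives 0.016, 0.367, 0.648 and 0.829, so all agree within 0.01.

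**4. If the same choice were carried into the model**

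This is hypothetical, since the model's N is not defined. The reading to watch is 50%.

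- Earlier data 1/30 at 12 µg and 4/30 at 25 µg (scenario 2 rows), 9 events at 50 µg: the current-dose probability is 0.41 with n=30 and 0.54 with n=27. A coarser grid gives 0.398 and 0.529. The 50% mark is crossed.
- Same earlier data, 4 events at 50 µg: the probability at 75 µg is 0.48 with n=20 and 0.51 with n=19. It is crossed by one missing diary.
- Earlier data 1/30 and 3/30, 9 events at 50 µg: the current-dose probability is 0.36 with n=30 and 0.49 with n=27. Not crossed.
- First group at 12 µg, 3 events: the next-dose probability is 0.593 with n=10 and 0.647 with n=9. Above 50% either way.

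A crossing can therefore occur, but only for particular counts close to the limit.

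**The case against.** The best defence is that the text can be read coherently. Section 4 already excludes people with missing values. Section 9.1.4 is the specific section for solicited AEs, and its diary restriction comes just before the severity sentence, so it can be taken as the rule for the whole section. The Safety Set sentence in 9.1 follows remarks on the display order of coded terms and may have been meant for coded AE tables. Table shells, which are not public, may settle the matter.

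Some of this stands. Section 8.1.1 most naturally follows section 4, and 9.1.4 may override 9.1. But section 4 yields where another rule is given, and 9.1 gives one. Section 9.1.2 then places solicited AEs in tables under that rule. Several defensible readings for a primary endpoint is the fault itself.

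Three stronger readings are tempting, and the documents do not support them:

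- A reader might infer that the primary percentages are calculated on the whole Safety Set. Section 8.1.1 does not say so.
- A reader might infer that the SAP declares a missing diary to be no reaction. No sentence does; it is only the arithmetic result of one rule. Gaps may also be filled: 9.1.4 accepts entries by the investigator and lets the investigator supply a grade that was not recorded, and protocol 6.1.1.5 has site staff review the diary at Days 4 and 8.
- A reader might infer that Grade 3 rates will be pulled under the 30% limit and escalation wrongly favoured. The SAP mentions neither the limit nor the model, and no SAP table is compared with 30%. The posterior probability informs the SRT and does not bind it. Holding rule 2b is a count of participants, so no denominator enters it.

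**Conclusion.** The point holds as a conflict between stated rules, plus an unstated denominator for the Grade 3 summary and the primary percentages. Where the Safety Set rule is applied, the reported rate equals the diary-based rate times the share of participants with diary data. At rates near 30%, that is a drop of about 1 to 3 percentage points for one to three missing diaries in a cohort of 30, and about 3 points for one missing in a group of 10.

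These sizes rest on assumed event counts and an assumed missing share. With complete diaries there is no difference, and the planned completion summary would let a reader see where one might arise. An effect on the SRT's model reading is possible, as step 4 of the working shows, but not established. It would need the same denominator choice to be used there and counts close to the threshold, and those runs leave out the age term. The matter should be settled before the tables are programmed, but it does not undermine the design.

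**What to change.** - **SAP 9.1 and 9.1.2:** exempt solicited AEs from the full Safety Set denominator.
- **SAP 8.1.1 and 9.1.4:** use one denominator for every solicited-AE percentage (any, each symptom, maximum severity). It should be Safety Set participants with at least one solicited-AE day completed by the participant or the investigator, which uses the SAP's existing definition of a completed day.
- **Tables:** show the Safety Set n and the number without diary data beside each percentage.
- **Appendix 13.3 model:** state that the same participants form N. The model is described only in the protocol, so this needs a cross-reference in the SAP or a clarification in the protocol. If SRT reviews have already been held, record which N they used.

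The cost is a few sentences and one extra row in the tables, with no new data. Rates rise slightly where diaries are missing. Under-reporting is reduced but not removed: a participant with one completed day and six blank ones is still treated as reaction-free on the blank days, so the completion summary should be read beside these tables.

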### **6.1.1.2 Eliciting and Documenting Adverse Events**

Adverse events will be reported throughout the study. Nonserious AEs will be reported from the time of the administration of IP until 28 days after the administration of IP; SAEs will be reported from the time the participant signs the ICF until exit from the study.

If the investigator learns of any SAE, including a death, at any time after a participant has been discharged from the study, and he/she considers the event to be reasonably related to the IP, the investigator must notify PPD Pharmacovigilance within 24 hours of learning of the event ([Section 6.1.1.3.1](#)).

At every study visit, participants will be asked a standard nonleading question to elicit any medically related changes in their well-being.

In addition to participant observations, AEs identified from any study data (eg, laboratory values, physical examination findings) or identified from review of other documents (eg, participant eDiaries) that are relevant to participant safety will be documented on the AE page in the eCRF.

As described in [Section 6.1.1.1.1](#), participant eDiaries will be used to collect solicited AEs.

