### **6.1.1.2.1 Assessment of Intensity**

The intensity, or severity, of an AE refers to the extent to which an AE affects the participant's daily activities.

Solicited AEs will be graded in intensity by the participant. The investigator will assess the maximum intensity that occurred over the duration of the event for all unsolicited AEs, including SAEs, recorded during the study. The assessment will be based on the investigator's clinical judgment.

The intensity of the following solicited events will be assessed as described in [Table 6-1](#).

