**Table 6-1** **Intensity Scales for Solicited Symptoms**

Event	Intensity Grade	Parameter
Pain at administration site	0	None
	1	Mild: Any pain neither interfering with nor preventing normal everyday activities
	2	Moderate: Painful when limb is moved and interferes with everyday activities
	3	Severe: Significant pain at rest. Prevents normal everyday activities
Redness at administration site	0	<2.5 cm
	1	2.5 – 5 cm
	2	5.1 – 10 cm
	3	>10 cm
Swelling at administration site	0	<2.5 cm
	1	2.5 – 5 cm and does not interfere with activity
	2	5.1 – 10 cm or interferes with activity
	3	>10 cm or prevents daily activity
Lymphadenopathy a	0	None
	1	Mild: No interference with activity
	2	Moderate: Some interference with daily activity or requires repeated use of non-narcotic pain reliever
	3	Severe: Prevents daily activity or requires use of narcotic pain reliever
Temperature b	0	<38.0°C or <100.4°F
	1	38.0 – 38.4°C or 100.4 – 101.1°F
	2	38.5 – 38.9°C or 101.2 – 102.0°F
	3	>38.9°C or >102.0°F
Headache	0	Normal
	1	Mild: Headache that is easily tolerated
	2	Moderate: Headache that interferes with normal activity
	3	Severe: Headache that prevents normal activity
Fatigue	0	Normal
	1	Mild: Fatigue that is easily tolerated
	2	Moderate: Fatigue that interferes with normal activity
	3	Severe: Fatigue that prevents normal activity
Myalgia	0	Normal
	1	Mild: No interference with daily activity
	2	Moderate: Interferes with daily activity
	3	Severe: Prevents daily activity
Arthralgia	0	Normal
	1	Mild: No interference with daily activity
	2	Moderate: Interferes with daily activity
	3	Severe: Prevents daily activity
Chills	0	None
	1	Mild sensation of cold; shivering; chattering of teeth
	2	Moderate tremor of the entire body; narcotics indicated
	3	Severe or prolonged, not responsive to narcotics

a. Defined as localized axillary, cervical or supraclavicular swelling or tenderness ipsilateral to the vaccination arm.

b. Refer to [Section 6.1.4](#) for the definition of fever.

The intensity of AEs will be assigned to one of the following categories:

- Grade 1 (Mild): An AE that is easily tolerated by the participant, causing minimal discomfort, and not interfering with everyday activities.
- Grade 2 (Moderate): An AE that is sufficiently discomforting to interfere with normal everyday activities.

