### **6.1.1.3 Reporting Adverse Events**

All AEs reported or observed during the study will be recorded on the AE page in the eCRF. Information to be collected includes, but is not limited to, the following:

- Event term
- Investigator-specified assessment of severity and causality to IP
- Seriousness/grade
- Time of onset of the event
- Time of resolution of the event
- Any required treatment or evaluations
- Outcome

Adverse events resulting from concurrent illnesses, reactions to concurrent illnesses, reactions to concurrent medications, or progression of disease states must also be reported. All AEs will be followed to adequate resolution. MedDRA will be used to code all AEs.

Any medical condition that is present at the time that the participant is screened but does not deteriorate should not be reported as an AE. However, if it deteriorates at any time during the study, it should be recorded as an AE.

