### 7.5.2 Analysis of the Primary Safety Endpoints

The primary safety endpoints as detailed in [Section 2](#) will be analyzed as described in the SAP. Laboratory abnormalities will be graded for severity following the FDA toxicity grading table ([Section 13.5](#)). For all safety endpoints, descriptive summary statistics will be provided for the Safety Set. Safety data listings will also be provided.

Refer to [Section 13.3](#) for details on Bayesian logistic regression used during the safety monitoring of the study.

In addition to the planned summary of SAEs throughout the study, any SAEs that are reported will also be summarized within 28 days of study vaccine administration.

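### SAP 9.1.4 replaces recorded participant grades with the investigator's in the solicited-AE severity summaries, departing from protocol 6.1.1.2.1, with no entry in SAP section 13 and no planned summary on the original grades

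*SAP*

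**What the plan says.** Protocol 6.1.1.2.1 is direct about who grades: "Solicited AEs will be graded in intensity by the participant". Its next sentence gives the investigator the intensity of unsolicited AEs, SAEs included.

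SAP 9.1.4 says that the investigator can overwrite the eDiary severity on the eCRF "if he believes the event grading has not been recorded, has been underestimated or overestimated, and provide his assessment". It then settles which value is tabulated: "When available the severity provided by the investigator will be used instead of the eDiary grading to generate the summaries of solicited events".

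For solicited AEs, SAP 9.1.4 plans a maximum-severity summary by dose group, a duration summary that includes days at each severity, a listing, and a percentage of eDiary days completed. SAP section 4 leaves display details to the table shells, which are not among the documents. SAP section 13, which is meant to hold changes to the planned analysis, deals only with assay results outside the quantification limits.

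**The concern.** The two documents name different graders for a grade that the participant has already recorded. The study is open-label (protocol 5.6), so the investigator who judges a grade too low or too high knows the dose. The participant knows it too, so neither grade is protected and the direction of any bias cannot be stated.

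What is at stake is how the Grade 3 rates by dose can be read. If only the adjusted grade is tabulated, and nothing shows how often or in which direction grades were changed, a reader cannot tell whether regrading by someone aware of the dose contributed to a difference between doses, or hid one.

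**Working it through.** The plan states no figure on this point, so there is none to reproduce. The check has two parts: a comparison of the texts, then the arithmetic of a single regrade.

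**Does any other section authorise the replacement?**

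- Protocol 6.1.1.2: AEs "identified from review of other documents (eg, participant eDiaries) that are relevant to participant safety will be documented on the AE page". This brings eDiary findings onto the eCRF. It does not say whose grade is then used.
- Protocol 6.1.1.3 lists, among the items for the AE page, "Investigator-specified assessment of severity and causality to IP". This is a general item and is silent on replacing a participant's solicited grade.
- SAP 9.1.2: "The severity of AEs (mild, moderate, severe) will be captured on the eCRF". Again a general statement on where severity is held.
- Protocol 7.5.2: the primary safety endpoints "will be analyzed as described in the SAP". This delegates analysis detail. It does not change the grader named in 6.1.1.2.1.

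None of the four authorises the replacement. The part of the SAP rule that fills an unrecorded grade conflicts little with the protocol; the part that replaces a recorded grade does.

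**Would the planned output reveal it?** The SAP text has one maximum-severity summary, on the adjusted grade. The eDiary completion percentage counts a day as complete whether the participant or the investigator entered it, so it cannot separate overrides. The listing is not said to carry both grades.

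**How much can one regrade move a rate?** Inputs: 30 per cohort and 10 to 20 per age group (protocol Table 3-1); 15 per Part B cohort (Table 3-3). Only a regrade across the Grade 3 boundary changes a Grade 3 rate, and the shift is 100/n percentage points:

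- n = 30: 100/30 = 3.3
- n = 20: 100/20 = 5.0
- n = 15: 100/15 = 6.7
- n = 10: 100/10 = 10.0

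For scale, take the rates behind the main prior component in protocol Appendix 3 (10% at 12 µg, 30% at 50 µg), with n = 30 and Clopper-Pearson 95% intervals:

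- 2/30 = 6.7% (0.8 to 22.1); 3/30 = 10.0% (2.1 to 26.5); 4/30 = 13.3% (3.8 to 30.7)
- 8/30 = 26.7% (12.3 to 45.9); 9/30 = 30.0% (14.7 to 49.4); 10/30 = 33.3% (17.3 to 52.8)

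The interval for 9/30 is 49.4 − 14.7 = 34.7 points wide, against a shift of 3.3 points. In a full cohort, one regrade is small beside sampling error.

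**Which denominator applies?** The maximum-severity summary is planned by dose group, so n = 30 is the relevant size for Cohorts 1 to 3. Smaller denominators arise in displays by age group, in Cohorts 4 and 5 if the two age groups receive different doses, and in Part B.

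**The case against.** The best defence is that protocol 6.1.1.2.1 says who grades, not which value is tabulated. The AE page asks for an investigator severity for AEs in general, so a solicited event may carry two grades, and choosing between them is a data convention that the protocol leaves to the SAP. On that view nothing planned was changed and section 13 had nothing to list. The rule is also stated openly in 9.1.4. This does not succeed: 6.1.1.2.1 divides grading explicitly between participant and investigator, and no section says that the second grade displaces the first. It does show that protocol 6.1.1.2.1 and 6.1.1.3 are unclear when read together.

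Other parts of the defence stand:

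- Table 6-1 defines Grades 0 to 3 for every solicited symptom, so there is a standard against which a grade could be judged too low or too high. The SAP does not refer to it at this point.
- Investigator input has merit for some scales. Grade 3 chills, for example, are "Severe or prolonged, not responsive to narcotics", which a participant may not judge well alone. Which grade should be main is a trade-off.
- The shells or the listing may show both grades. The gap is in what the SAP text commits to.

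A reader might infer more than the documents support in three ways. First, that the primary solicited-AE endpoint is compromised. That endpoint is the percentage with each event, and it changes only if a grade moves to or from 0 or a missing entry is filled. Second, that differences between doses could swing by 20 points. That needs one downgrade in one group and one upgrade in another, both across the Grade 3 boundary and both at n = 10 (200/10); at n = 30 the same pair gives 6.7 points. Third, that regrading alters dose escalation or a study hold. The Appendix 3 model and holding rule 2b both count Grade 3 solicited AEs, but neither says whose grade is used, so no effect there is established.

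**Conclusion.** The point holds in a limited form. SAP 9.1.4 replaces a recorded participant grade, protocol 6.1.1.2.1 assigns that grade to the participant, section 13 is silent, and the SAP text provides no override count and no summary on the original grades.

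The consequence is confined to the maximum-severity (Grade 3) and duration-by-severity summaries. It is 3.3 points per boundary-crossing regrade in a dose group of 30, and up to 10 points in an age group of 10. These are sizes per event, not expected effects: the documents give no override rate, so no probability of a changed result is claimed, and the direction of bias is unknown. The study is descriptive, with no hypothesis testing, so no test or error rate is affected. This should be fixed because it concerns how open-label Grade 3 rates are read and the remedy is cheap, not because harm has been shown.

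**What to change.** Reconcile protocol 6.1.1.2.1 and 6.1.1.3 with SAP 9.1.4. Then, in SAP 9.1.4:

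1. Produce the maximum-severity summary twice: on the eDiary grade, with the investigator's grade only where the eDiary grade is missing, and on the investigator-adjusted grade. State which is main. The eDiary version is the one that follows 6.1.1.2.1.
2. Add a participant-versus-investigator shift table (upgrades, downgrades, filled entries) by dose and age group.
3. If the override stays in the main tables, tie under- and overestimation to Table 6-1 and record the change in section 13.
4. Repeat the duration-by-severity summary only if daily grades exist under both versions.

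For the Appendix 3 model and holding rule 2b, only reconcile the protocol text so that it states whose grade is used.

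The cost is a short SAP revision and one or two extra tables. SAP 9.1.4 speaks of the two grades as separate values, so both should be retrievable, but the sponsor should confirm that overwriting keeps the original. The downside is that implausible participant entries stay visible in the eDiary-based table, where the adjusted version and the shift table would explain them.
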